8.6 Methods of Measurement

The same method of assessment and the same technique should be used to characterize each identified and reported lesion at baseline and during follow-up. Assessments should be identified on a calendar schedule and should not be affected by delays in therapy, which may be treatment arm dependent. While on study, all lesions recorded at baseline should have their actual measurements recorded at each subsequent evaluation, even when very small (e.g. 2 mm). If it is the opinion of the radiologist that the lesion has likely disappeared, the measurement should be recorded as 0 mm. If the lesion is believed to be present and is faintly seen but too small to measure, a default value of 5 mm should be assigned. For lesions which fragment/split add together the longest diameters of the fragmented portions; for lesions which coalesce, measure the maximal longest diameter for the “merged lesion”.

- 8.6.1 **Clinical Lesions.** Clinical lesions will only be considered measurable when they are superficial and ≥ 10 mm as assessed using calipers (e.g. skin nodules). For the case of skin lesions, documentation by colour photography including a ruler to estimate the size of the lesion is recommended. If feasible, imaging is preferred.
- 8.6.2 **Chest X-ray.** Chest CT is preferred over chest X-ray, particularly when progression is an important endpoint, since CT is more sensitive than X-ray, particularly in identifying new lesions. However, lesions ≥ 20 mm on chest X-ray may be considered measurable if they are clearly defined and surrounded by aerated lung.
- 8.6.3 **CT, MRI.** CT is the best currently available and reproducible method to measure lesions selected for response assessment. This guideline has defined measurability of lesions on CT scan based on the assumption that CT slice thickness is 5 mm or less. When CT scans have slice thickness greater than 5 mm, the minimum size for a measurable lesion should be twice the slice thickness. MRI is also acceptable in certain situations (e.g. for body scans). Other specialized imaging or other techniques may also be appropriate for individual case [Eisenhauer 2009]. For example, while PET scans are not considered adequate to measure lesions, PET-CT scans may be used providing that the measures are obtained from the CT scan and the CT scan is of identical diagnostic quality to a diagnostic CT (with IV and oral contrast).
- 8.6.4 **Bone Scan.** 99m Tc-methylene diphosphonate radionuclide bone scintigraphy is the standard for bone imaging.
- 8.6.5 **Ultrasound.** Ultrasound is not useful in assessment of lesion size and should not be used as a method of measurement. If new lesions are identified by ultrasound in the course of the study, confirmation by CT is advised.
- 8.6.6 **Endoscopy, Laparoscopy.** The utilization of these techniques for objective tumour evaluation is not advised. However, they can be useful to confirm complete pathological response when biopsies are obtained or to determine relapse in trials where recurrence following complete response or surgical resection is an endpoint.
- 8.6.7 **Tumour Markers.** Tumour markers alone cannot be used to assess objective tumour response. If markers are initially above the upper normal limit, however, they must normalize for a patient to be considered in complete response.

8.6.8 *Cytology, Histology*. These techniques can be used to differentiate between PR and CR in rare cases if required by protocol (for example, residual lesions in tumour types such as germ cell tumours, where known residual benign tumours can remain). When effusions are known to be a potential adverse effect of treatment (e.g. with certain taxane compounds or angiogenesis inhibitors), the cytological confirmation of the neoplastic origin of any effusion that appears or worsens during treatment when the measurable tumour has met criteria for response or stable disease is advised to differentiate between response or stable disease and progressive disease.

9.0 SERIOUS ADVERSE EVENT REPORTING

The descriptions and grading scales found in the NCI Common Terminology Criteria for Adverse Events (CTCAE) will be utilized for Adverse Event (AE) reporting (version can be found in Appendix V). All appropriate treatment areas should have access to a copy of the CTCAE. A copy of the CTCAE can be downloaded from the CTEP web site: (http://ctep.cancer.gov/protocolDevelopment/electronic_applications/ctc.htm).

All serious adverse events (SAE) defined as per ICH guidelines (see below) and other adverse events must be recorded on case report forms. In addition, all “reportable” serious adverse events are subject to expedited reporting using the CCTG SAE form. The term ‘reportable SAE’ is used in the definitions which follow to describe those SAEs which are subject to expedited reporting to CCTG.

9.1 Definition of a Reportable Serious Adverse Event

- All serious adverse events, regardless of whether they are unexpected or related to protocol treatment, occurring during the treatment period and within 30 days after the last protocol treatment administration, must be reported in an expedited manner. Any late serious adverse event occurring after this 30-day period which is unexpected and related to protocol treatment must also be reported in an expedited manner (see Section 9.2 for reporting instructions).
- A serious adverse event (SAE) is any adverse event that at any dose:
 - results in death
 - is life-threatening
 - requires inpatient hospitalization or prolongation of existing hospitalization (excluding hospital admissions for study drug administration, transfusional support, scheduled elective surgery and admissions for palliative or terminal care)
 - results in persistent or significant disability or incapacity
 - is a congenital anomaly/birth defect
- Any immune related adverse event (irAE) requiring high dose steroids is by definition medically significant and must be reported as such.
- If a patient shows an AST or ALT $\geq 3 \times$ ULN together with total bilirubin $\geq 2 \times$ ULN, refer to Appendix II for further instructions on cases of increases in liver biochemistry and evaluation of Hy’s Law. These cases should be reported as SAEs if, after evaluation, they meet the criteria for a Hy’s law case or if any of the individual liver test parameters fulfill any of the SAE criteria.

Medical and scientific judgement should be exercised in deciding whether expedited reporting is appropriate in other situations such as important medical events that may not be immediately life-threatening or result in death or hospitalization but may jeopardize the patient or may require intervention to prevent one of the events listed above.

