4.1.9 Laboratory Requirements

(Must be done within 7 days prior to randomization)

Hematology	Absolute neutrophils	$\geq 1.5 \times 10^9/L$
	Platelets	$\geq 100 \times 10^9/L$
	Hemoglobin	$\geq 90 \text{ g/L}^*$
Chemistry	Bilirubin	$\leq 1.5 \times \text{ULN}$ (upper limit of normal)**
	AST and ALT	$\leq 2.5 \times \text{ULN}$ $\leq 5.0 \times \text{ULN}$ (if patient has liver metastases)
	Serum creatinine or: Creatinine clearance***	$\leq 1.25 \times \text{ULN}$ $\geq 40 \text{ mL/min}$

$*$ Contact CCTG if exception on medical grounds is appropriate to minimize risk of unnecessary transfusion.
 $**$ If confirmed Gilbert's, eligible provided $\leq 3 \times \text{ULN}$.
 $***$ Creatinine clearance to be measured directly by 24 hour urine sampling or as calculated by Cockcroft and Gault equation below:
 Males: GFR = $\frac{1.23 \times (140-\text{age}) \times \text{weight in kg}}{\text{serum creatinine in } \mu\text{mol/L}}$

4.1.10 Non-sterilized male patients who are sexually active with a female partner of childbearing potential must use male condom plus spermicide while on study and for 6 months after the last dose of durvalumab and tremelimumab, or for 3 months after the last dose of durvalumab alone. Female partners of a male subject must use a highly effective method of contraception throughout this period. See Section 9.3.1 for additional details.

Male patients should also refrain from donating sperm during the study and for 6 months after the last dose of durvalumab and tremelimumab or for 3 months after the last dose of durvalumab alone.

4.1.11 Subjects should not donate blood while participating in this study, or for at least 90 days following the last infusion of durvalumab or tremelimumab.

4.1.12 Patient consent must be appropriately obtained in accordance with applicable local and regulatory requirements. Each patient must sign a consent form prior to enrollment in the trial to document their willingness to participate.

Patients who cannot give informed consent (i.e. mentally incompetent patients, or those physically incapacitated such as comatose patients) are not to be recruited into the study. Patients competent but physically unable to sign the consent form may have the document signed by their nearest relative or legal guardian. Each patient will be provided with a full explanation of the study before consent is requested.

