10.4 Follow-up Off Protocol Treatment

All patients will be seen at 4 weeks after completion of protocol therapy. For patients who go off protocol treatment with iCPD, and have ongoing toxicities (until resolved to \leq grade 2) and late toxicities (including second malignancies) follow-up will be required every 3 months.

For patients with no ongoing or late toxicities and have confirmed disease progression, follow-up will be required every 6 months for survival data and other anti-cancer treatment only. For patients who go off protocol treatment with CR/ICR, PR/iPR, SD/iSD or iUPD ongoing, and have not already started other systemic therapy follow-up will be required every 3 months until relapse (see Section 5.0 for investigations to be performed) and then every 6 months until death.

Death Report will be required for all patients, due within 2 weeks of knowledge of death (see Appendix IV - Documentation for Study).

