APPENDIX IV - DOCUMENTATION FOR STUDY

Follow-up is required for patients from the time of randomization and will apply to all eligible and ineligible patients. This trial will use a web-based Electronic Data Capture (EDC) system for all data collection including SAE reporting (see Section 9.0 for details regarding SAE reporting). For details about accessing the EDC system and completing the on-line Case Report Forms, please refer to the Data Management Guidebook posted on the IND.232 area of the CCTG web-site (www.ctg.queensu.ca).

The ELECTRONIC CRFs to be used in this trial are:

Electronic Case Report Form	To be Completed/Submitted Electronically:	Supporting Documentation to be sent using Supporting Document Upload Tool*
BASELINE REPORT	Due within 2 weeks of patient registration.	Copies of signature pages of main and optional consent forms; relevant pathology & radiology reports.
TREATMENT REPORT	To be completed every 4 weeks (i.e. after each cycle). Due within 2 weeks of end of course. This report documents treatment, adverse events, investigations and response assessment for each course.	Relevant radiology reports.
CORRELATIVE STUDIES	See Section 12.0.	
END OF TREATMENT REPORT	To be completed when patient goes off protocol treatment. Due within 2 weeks of end of protocol treatment.	
4 WEEK POST TREATMENT REPORT	To be completed once on all patients, 4 weeks after the end of the last cycle date. Due within 2 weeks after contact with patient.	Relevant radiology reports.
3 MONTH FOLLOW-UP REPORT	Continued in-person follow-up is not required for patients who go off protocol treatment with progressive disease , except to document ongoing toxicities (until resolved to \leq grade 2) and late toxicities (including second malignancies). For patients who go off protocol treatment with response , stable disease or unconfirmed progression ongoing , Follow-up Report to be completed every 3 months until relapse/progression. Due within 2 weeks after contact with patient.	Relevant radiology reports.
6 MONTH FOLLOW-UP REPORT	Required for all patients with confirmed PD to confirm survival status and other anticancer treatment.	
RELAPSE/PROGRESSION REPORT	To be completed at the time of disease relapse or progression. Due within 2 weeks after contact with patient.	Relevant radiology reports.

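### Late related immune-mediated SAEs are likely to be under-captured: after day 30 the general rule needs them to be unexpected, and confirmed-PD patients without toxicity have no later scheduled AE contact

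*Combined protocol and SAP*

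**What the plan says.** Section 9.1 sets two reporting periods. In the first, all SAEs, whatever their cause, "occurring during the treatment period and within 30 days after the last protocol treatment administration, must be reported in an expedited manner". In the second, with no end date, "Any late serious adverse event occurring after this 30-day period which is unexpected and related to protocol treatment must also be reported". A separate bullet in 9.1 adds: "Any immune related adverse event (irAE) requiring high dose steroids is by definition medically significant and must be reported as such". That bullet gives neither a time limit nor a definition of high dose.

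On follow-up, section 10.4 states: "All patients will be seen at 4 weeks after completion of protocol therapy". Appendix IV times the same report at "4 weeks after the end of the last cycle date". Under 10.4, patients with confirmed progression who have ongoing or late toxicities are followed every 3 months. For those with neither, "follow-up will be required every 6 months for survival data and other anti-cancer treatment only". In the section 5.0 flowsheet, the adverse-event row has entries at the 4-week and 3-month visits and none in the 6-month column.

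Section 9.0 has SAEs and other adverse events recorded on case report forms and gives no end date. Toxicity and tolerability are a secondary objective (1.2, 13.1).

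**The concern.** The late toxicity of most interest with these two antibodies is immune-mediated, and the protocol itself names the main events as known risks. The late-reporting rule turns on unexpectedness, so it works least well for that class of event. The natural safeguard would be a scheduled contact at which patients are asked about new events, but one group has none after the 4-week visit. Treatment runs until progression or unacceptable toxicity (7.2, 10.2), so that group may be large, although the documents give no proportion.

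At stake is the completeness of the toxicity description in each arm, and of the data that the central office monitors under 13.4. Under 9.5 the drug supplier is notified of SAEs reportable under 9.1, so an event outside 9.1 does not reach the supplier by that route either. The primary endpoint is not affected.

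**Working it through.** The plan has no figure of its own to reproduce. The check is a comparison of rules and dates, with the last infusion as day 0.

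**1. Timeline.** Inputs: the all-SAE window of 30 days (9.1), the 4-week cycle with dosing on its first day (7.1.1), and the two statements of the 4-week visit.

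- Reading A, 4 weeks after the last infusion (one reading of 5.0 and 10.4): day 28. This is 30 − 28 = 2 days before the all-SAE window closes.
- Reading B, 4 weeks after the end of the last cycle (Appendix IV): 28 + 28 = day 56. This is 56 − 30 = 26 days after the window closes.
- Difference between the readings: 56 − 28 = 28 days.

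**2. The 9.1 rule applied to a late event.** Take a serious colitis on day 45, judged related. It is past day 30, so the general rule asks whether it is unexpected. Sections 3.1.6 and 7.1.4 list colitis. If expectedness follows known risks, the event is expected and this rule does not require a report. Section 9.4 uses the same three conditions (serious, unexpected, related) for reports to Health Canada. Section 9.1 applies the unexpectedness condition one step earlier, between site and sponsor.

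**3. Scheduled AE assessment after treatment.**

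| Patient off treatment | Contact after the 4-week visit | AE assessment scheduled? |
|---|---|---|
| No confirmed PD, no new systemic therapy | Every 3 months until relapse (10.4) | Entry in the 5.0 row, footnoted to related events until they settle |
| Confirmed PD, ongoing or late toxicity | Every 3 months (10.4, Appendix IV) | Yes, though the 5.0 column header can be read otherwise |
| Confirmed PD, neither | Every 6 months (10.4, Appendix IV) | No |

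For the third row, the day-45 colitis would come up at the visit under reading B but not under reading A. An event starting after day 56 has no scheduled AE assessment under either reading.

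**4. Other routes.** Three provisions could still bring in such an event: case-report-form recording (9.0), the high-dose-steroid bullet (9.1) and 3-monthly follow-up of late toxicity (10.4). Each operates once the site knows of the event. None schedules a contact to look for a new one.

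**5. What one added contact would cover.** With an illustrative contact at day 90, the further time asked about is 90 − 28 = 62 days under reading A, or 90 − 56 = 34 days under reading B.

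**The case against.** The best counter-argument is the steroid bullet. It carries no time limit and no expectedness test, and 7.1.5 directs prompt systemic steroids for severe immune events, so many serious late cases could come under it. Section 9.0 also keeps case-report-form recording open, unexpected related SAEs stay reportable indefinitely, deaths are reported with their cause (Appendix IV), and patients agree to return for adverse events during the trial (4.1.13). In addition, completion of therapy can be read as the end of the last cycle, which would bring 10.4 into line with Appendix IV.

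Most of this stands, and it narrows the gap. It does not close it: whether the steroid bullet applies after day 30 is not stated, high dose is undefined, and all these routes depend on the site hearing of the event unprompted.

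A reader might infer more than the text supports:

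- **That safety collection ends at day 30.** It does not. Day 30 ends expedited reporting of SAEs regardless of cause.
- **That every patient with confirmed progression gets survival-only contact.** Those with ongoing or late toxicity are followed every 3 months.
- **That the protocol's own precautions set the proper safety window.** Contraception runs "for 6 months after the last dose of durvalumab and tremelimumab, or for 3 months after the last dose of durvalumab alone" (4.1.10) and blood donation is barred "for at least 90 days following the last infusion of durvalumab or tremelimumab" (4.1.11). These concern reproduction and donation, and the live-vaccine precaution after durvalumab is 30 days (7.3.2). They are not a toxicity-observation standard, so they support neither a percentage of unobserved time nor a claim that the combination arm is worse affected.
- **That a patient progressing at the first scan, at week 12, goes almost wholly unobserved.** Section 10.1 keeps clinically stable patients with unconfirmed progression on treatment until the next assessment.

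**Conclusion.** The point holds in limited form. Late, related, serious immune events can fall outside the general rule in 9.1, and patients with confirmed progression and no toxicity at the 4-week visit have no later scheduled AE assessment. Under-capture of late immune toxicity is the likely result. To say that such toxicity is missed would go too far, given the remaining routes.

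The size cannot be put as a number of events. Planned enrolment is 24 to 74 (13.1), but the documents give neither the share leaving with confirmed progression nor a rate of late immune events, so any count would rest on unsourced rates. What can be stated is that the last scheduled AE assessment for this group is at day 28 or day 56, a 28-day difference that depends on the section followed.

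The first part assumes that expectedness is judged against known risks. The protocol names no reference for it, and the Investigator Brochures are not available here. The second part, on scheduled contact, does not need that assumption.

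**What to change.** 1. In 9.1, remove the unexpectedness condition from the late-SAE sentence so that any related late SAE is reported. State that the high-dose-steroid bullet also applies after day 30.
2. In 5.0, 10.4 and Appendix IV, add one telephone contact asking about adverse and immune-related events, at a fixed time after the last infusion (for example about 90 days), for all treated patients, including those with confirmed progression. Subsequent anti-cancer treatment is already collected and can be used for attribution.
3. Define the 4-week visit once, reconciling 5.0 and 10.4 with Appendix IV, so that it does not fall before the 30-day all-SAE window closes. Reconcile the 3-month column header in 5.0 with 10.4 and Appendix IV for patients with confirmed progression and toxicity.

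The cost is protocol wording, one call per patient and a few more late entries. Some late events will occur on next-line therapy and need attribution. No extra staff or procedures are needed.

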9.2 Serious Adverse Event Reporting Instructions

All reportable serious adverse events must be reported using a web-based Electronic Data Capture (EDC) system being used for this trial. For details about accessing the EDC system and completing the on-line SAE report form, please refer to the CCTG Generic Data Management Guidebook for EDC Studies posted on the IND.232 section of the CCTG website (www.ctg.queensu.ca).

Within 24 hours: Complete preliminary Serious Adverse Event Report and submit to CCTG via EDC system.

Within 7 days: Update Serious Adverse Event Report as much as possible and submit report to CCTG via EDC system.

EDC SAE web application interruption:

In the rare event that internet connectivity to the EDC SAE system is disrupted, please print and complete a paper copy of the SAE Report, available from the trial specific website.

FAX paper SAE Report to:

IND.232 Study Coordinator
Canadian Cancer Trials Group
[contact]

Please use the same timelines for submission as for direct EDC reporting.

Once internet connectivity is restored, the information that was FAXED to CCTG on the paper SAE Report must also be entered by the site into the EDC SAE web application.

Local internet interruption:

If you are unable to access the EDC SAE system, and cannot access a paper copy of the SAE Report from the trial website, please phone the IND.232 trial team [contact]) to obtain a copy of the SAE Report by FAX. Once completed, the report must be FAXED back to CCTG as indicated above. Once internet connectivity is restored, the information that was FAXED to CCTG on the paper SAE Report must also be entered by the site into the EDC SAE web application.

In cases of prolonged internet interruptions, please contact the CCTG Safety Desk for further instructions [contact]).

9.3 Other Protocol Reportable Events – Pregnancy Reporting

9.3.1 Pregnancy Prevention

Males who are enrolled in the trial must have agreed to use contraceptive method(s) as described in Eligibility Criterion 4.1.10. Investigators may wish to additionally advise the female partners of male participants about pregnancy prevention guidelines when appropriate and compliant with local policy.

Not engaging in sexual activity for the total duration of the trial and the drug washout period is an acceptable practice; however, occasional abstinence, the rhythm method, and the withdrawal method are not acceptable methods of contraception. However, if at any point a previously celibate patient chooses to become heterosexually active during the time period for use of contraceptive measures outlined in the protocol, he is responsible for beginning contraceptive measures.

Females of childbearing potential are defined as those who are not surgically sterile (i.e. bilateral tubal ligation, bilateral oophorectomy, or complete hysterectomy) or post-menopausal (defined as 12 months with no menses without an alternative medical cause).

A highly effective method of contraception is defined as one that results in a low failure rate (i.e. less than 1% per year) when used consistently and correctly. Highly effective methods of contraception are described in the table below. Note that some contraception methods are not considered highly effective (e.g. male or female condom with or without spermicide; female cap, diaphragm, or sponge with or without spermicide; non-copper containing intrauterine device; progestogen-only oral hormonal contraceptive pills where inhibition of ovulation is not the primary mode of action [excluding Cerazette/desogestrel which is considered highly effective]; and triphasic combined oral contraceptive pills).

Highly Effective* Methods of Contraception

Barrier/Intrauterine Methods	Hormonal Methods

• Copper T intrauterine device• Levonorgesterel-releasing intrauterine system (e.g. Mirena®)**	
• Etonogestrel implants: e.g. Implanon or Norplan• Intravaginal device: e.g. ethinylestradiol and etonogestrel• Medroxyprogesterone injection: e.g. Depo-Provera• Normal and low dose combined oral contraceptive pill• Norelgestromin/ethinylestradiol transdermal system• Cerazette (desogestrel)

* Highly effective (i.e. failure rate of <1% per year).
** This is also considered a hormonal method.

